10.1.6 Response Review

Central review of staging scan will not be performed.

11 ADVERSE EVENT REPORTING REQUIREMENTS

11.1 Definitions

Adverse Event (AE)

Dana-Farber Cancer Institute/Harvard Cancer Care guidelines for reporting SAEs should be followed, including the guidelines for gene transfer studies. (<http://www.dana-farber.org/res/OPRS/advevent/default.asp>). These guidelines require the following events to be reported to the DFCI IRB: (1) Grade 2 (moderate) and Grade 3 (serious) events that are unexpected and possibly, probably, or definitely related/associated with the intervention; (2) all Grade 4 (life threatening) events, and (3) all Grade 5 (fatal) events, occurring while the subject is enrolled and actively participating in the trial, or when the event occurred within 30 days of the last study intervention. In accordance to these guidelines, the following steps will be taken to report a SAE:

Serious adverse event (SAE)

A serious adverse event (SAE) is any adverse event, occurring at any dose and regardless of causality that:

- Results in death
- Is life-threatening. Life-threatening means that the person was at immediate risk of death from the reaction as it occurred, i.e., it does not include a reaction which hypothetically might have caused death had it occurred in a more severe form.
- Requires or prolongs inpatient hospitalization (i.e., the event required at least a 24-hour hospitalization or prolonged a hospitalization beyond the expected length of stay). Hospitalization admissions and/or surgical operations scheduled to occur during the study period, but planned prior to study entry are not considered SAEs if the illness or disease existed before the person was enrolled in the trial, provided that it did not deteriorate in an unexpected manner during the trial (e.g., surgery performed earlier than planned).
- Results in persistent or significant disability/incapacity. Disability is defined as a substantial disruption of a person's ability to conduct normal life functions.
- In a congenital anomaly or birth defect; or
- Is an important medical event when, based upon appropriate medical judgment, it may jeopardize the participant and require medical or surgical intervention to prevent one of the outcomes listed above. Examples of such medical events include allergic bronchospasm requiring intensive treatment in an emergency room or at home; blood dyscrasias or convulsions that do not result in inpatient hospitalization, or the development of drug dependency or drug abuse.

Events **not** considered to be serious adverse events are hospitalizations for:

- routine treatment or monitoring of the studied indication, not associated with any deterioration in condition, or for elective procedures
- elective or pre-planned treatment for a pre-existing condition that did not worsen
- emergency outpatient treatment for an event not fulfilling the serious criteria outlined above and not resulting in inpatient admission
- respite care

Expectedness

Adverse events can be 'Expected' or 'Unexpected.'

Expected adverse event

Expected adverse events are those that have been previously identified as resulting from administration of the agent. For the purposes of this study, an adverse event is considered expected when it appears in the current adverse event list, the Investigator's Brochure, the package insert or is included in the informed consent document as a potential risk.

Refer to Section 6.1 for a listing of expected adverse events associated with the study agent(s).

Unexpected adverse event

For the purposes of this study, an adverse event is considered unexpected when it varies in nature, intensity or frequency from information provided in the current adverse event list, the Investigator's Brochure, the package insert or when it is not included in the informed consent document as a potential risk.

Attribution

Attribution is the relationship between an adverse event or serious adverse event and the study treatment. Attribution will be assigned as follows:

- Definite – The AE is clearly related to the study treatment.
- Probable – The AE is likely related to the study treatment.
- Possible – The AE may be related to the study treatment.
- Unlikely - The AE is doubtfully related to the study treatment.
- Unrelated - The AE is clearly NOT related to the study treatment.

11.2 Procedures for AE and SAE Recording and Reporting

Participating investigators will assess the occurrence of AEs and SAEs at all participant evaluation time points during the study.

All AEs and SAEs whether reported by the participant, discovered during questioning, directly observed, or detected by physical examination, laboratory test or other means, will be recorded in the participant's medical record and on the appropriate study-specific case report forms.

The descriptions and grading scales found in the revised NCI Common Terminology Criteria for Adverse Events (CTCAE) version 4.0 will be utilized for AE reporting. All appropriate treatment areas should have access to a copy of the CTCAE version 4.0. A copy of the CTCAE version 4.0 can be downloaded from the CTEP website at:

http://ctep.cancer.gov/protocolDevelopment/electronic_applications/ctc.htm.

11.3 Reporting Requirements

All life-threatening events which may be due to vaccine administration

All fatal events while on study

All such events will be reported to the DFCI Office for the Protection of Research Subjects by the protocol chairperson within 48 hours.

11.4 Reporting to the Principal Investigator

11.4.1 Serious Adverse Event Reporting

All serious adverse events that occur after the initial dose of study treatment, during treatment, or within 30 days of the last dose of treatment must be reported to the DF/HCC Overall Principal Investigator on the local institutional SAE form. This includes events meeting the criteria outlined in Section 9.1, as well as the following:

- Grade 2 (moderate) and Grade 3 (severe) Events – Only events that are unexpected and possibly, probably or definitely related/associated with the intervention.
- All Grade 4 (life-threatening or disabling) Events – Unless expected AND specifically listed in the protocol as not requiring reporting.
- All Grade 5 (fatal) Events – When the participant is enrolled and actively participating in the trial OR when the event occurs within 30 days of the last study intervention.

Note: If the participant is in long term follow up, report the death at the time of continuing review.

Participating investigators must report each serious adverse event to the DF/HCC Overall Principal Investigator within 24 hours of learning of the occurrence. In the event that the participating investigator does not become aware of the serious adverse event immediately (e.g., participant sought treatment elsewhere), the participating investigator is to report the event within 24 hours after learning of it and document the time of his or her first awareness of the adverse event. Report serious adverse events by telephone, email or facsimile to:

[name].
[contact]
[contact]
[contact]

Within the following 24-48 hours, the participating investigator must provide follow-up information on the serious adverse event. Follow-up information should describe whether the event has resolved or continues, if and how the event was treated, and whether the participant will continue or discontinue study participation.

11.4.2 Non-Serious Adverse Event Reporting

Non-serious adverse events will be reported to the DF/HCC Overall Principal Investigator on the toxicity Case Report Forms.

11.5 Reporting to the IND Sponsor

Adverse events meeting the following criteria, regardless of relatedness or expectedness, must be reported to the IND Sponsor (or designee) for those subjects who received at least 1 vaccine:

- Grade ≥ 3 Non-Hematologic
- Grade ≥ 3 Hematologic
- All Grade 5 events

Reporting to the Sponsor begins at time of first vaccine and goes until 15 years after the subject's last vaccine.

All events meeting the criteria above must be forwarded to the IND Sponsor (or designee) within 2 business days of knowledge of the event using an FDA Form 3500A.

11.6 Reporting to the Institutional Review Board (IRB)

Investigative sites within DF/HCC will report all serious adverse events directly to the DFCI Office for Human Research Studies (OHRS).

11.7 Reporting to the Food and Drug Administration (FDA)

[name] as holder of the IND (IND Sponsor), will be responsible for all communication with the FDA. The IND Sponsor will report to the FDA, regardless of the site of occurrence, any adverse event that is serious, unexpected and reasonably related (i.e., possible, probable, definite) to the study treatment.

Unexpected fatal or life-threatening experiences associated with the use of the study treatment will be reported to FDA as soon as possible but in no event later than 7 calendar days after initial receipt of the information.

All other serious unexpected experiences associated with the use of the study treatment will be reported to FDA as soon as possible but in no event later than 15 calendar days after initial receipt of the information.

Events will be reported to the FDA by telephone ([name]) or by fax ([name]) using Form FDA 3500A (Mandatory Reporting Form for investigational agents) or FDA Form 3500 (Voluntary Reporting Form for commercial agents). Forms are available at <http://www.fda.gov/medwatch/getforms.htm>.

11.8 Reporting to the NIH Office of Biotechnology Activities (OBA)

The IND Sponsor will be responsible for all communication with OBA. The IND Sponsor will report to OBA, regardless of the site of occurrence, any adverse event that is serious, unexpected and reasonably related (i.e., possible, probable, definite) to the gene transfer product.

Unexpected fatal or life-threatening experiences associated with the use of the gene transfer product will be reported to OBA as soon as possible but in no event later than 7 calendar days after initial receipt of the information (i.e., at the same time the event is reported to FDA).

All other serious unexpected experiences associated with the use of the gene transfer product will be reported to OBA as soon as possible but in no event later than 15 calendar days after initial receipt of the information (i.e., at the same time the event is reported to FDA).

The serious adverse event report must include: (1) the date of the event; (2) designation of the report as an initial report or a follow-up report, identification of all safety reports previously filed for the clinical protocol concerning a similar adverse event, and an analysis of the significance of the adverse event in light of previous similar reports; (3) clinical site; (4) the Principal Investigator; (5) NIH Protocol number; (6) FDA's Investigational New Drug (IND) Application number; (7) vector type, e.g., adenovirus; (8) vector subtype, e.g., type 5, relevant deletions; (9) gene delivery method, e.g., *in vivo*, *ex vivo* transduction; (10) route of administration, e.g., intratumoral, intravenous; (11) dosing schedule; (12) a complete description of the event; (13) relevant clinical observations; (14) relevant clinical history; (15) relevant tests that were or are planned to be conducted; (16) date of any treatment of the event; and (17) the suspected cause of the event. These items may be reported on the Form FDA 3500A, or other means provided that all of the above elements are specifically included.

11.9 Reporting to the Institutional Biosafety Committee (IBC)

The Overall Principal Investigator will report to the IBC any adverse event that is serious, unexpected and reasonably related (i.e., possible, probable, definite) to the gene transfer product, provided that the event occurred at their investigative site.

Unexpected fatal or life-threatening experiences associated with the use of the gene transfer product will be reported to the IBC as soon as possible but in no event later than 7 calendar days after initial receipt of the information.

All other serious unexpected experiences associated with the use of the gene transfer product will be reported to the IBC as soon as possible but in no event later than 15 calendar days after initial receipt of the information.

Copies of all IBC submissions should be emailed to the IND Sponsor (or designee) within 2 business days of submission.

Participating investigators should obtain from the IND Sponsor a copy of the adverse event report submitted to the FDA and OBA, and forward this information to their respective IBC as soon as possible.

11.10 Reporting to Hospital Risk Management

Participating investigators will report to their local Risk Management office any subject safety reports or sentinel events that require reporting according to institutional policy.

11.11 Monitoring of Adverse Events and Period of Observation

All adverse events, both serious and non-serious, and deaths that are encountered from initiation of study intervention, throughout the study, and within 30 days of the last study intervention should be followed to their resolution, or until the participating investigator assesses them as stable, or the participating investigator determines the event to be irreversible, or the participant is lost to follow-up. The presence and resolution of AEs and SAEs (with dates) should be documented on the appropriate case report form and recorded in the participant's medical record to facilitate source data verification.

For some SAEs, the study sponsor or designee may follow-up by telephone, fax, and/or monitoring visit to obtain additional case details deemed necessary to appropriately evaluate the SAE report (e.g., hospital discharge summary, consultant report, or autopsy report).

Participants should be instructed to report any serious post-study event(s) that might reasonably be related to participation in this study. Participating investigators should notify the DF/HCC Overall Principal Investigator and their respective IRB of any unanticipated death or adverse event occurring after a participant has discontinued or terminated study participation that may reasonably be related to the study.

12. DATA AND SAFETY MONITORING

12.1 Data Reporting

12.1.1 Method

The QACT will collect, manage, and monitor data for this study.

12.1.2 Data Submission

The schedule for completion and submission of case report forms (paper or electronic) to the QACT is as follows:

Form	Submission Timeline
Eligibility Checklist	Complete prior to registration with QACT
On Study Form	Within 14 days of registration
Baseline Assessment Form	Within 14 days of registration
Treatment Form	Within 10 days of the last day of the cycle
Adverse Event Report Form	Within 10 days of the last day of the cycle
Response Assessment Form	Within 10 days of the completion of the cycle required for response evaluation
Off Treatment/Off Study Form	Within 14 days of completing treatment or being taken off study for any reason
Follow up/Survival Form	Within 14 days of the protocol defined follow up visit date or call

12.2 Safety Meetings

The DF/HCC Data and Safety Monitoring Committee (DSMC) will review and monitor toxicity and accrual data from this trial. The committee is composed of clinical specialists with experience in oncology and who have no direct relationship with the study. Information that raises any questions about participant safety will be addressed with the Principal Investigator and study team.

The DSMC will meet quarterly and/or more often if required to review toxicity and accrual data. Information to be provided to the committee may include: up-to-date participant accrual; current dose level information; DLT information; all grade 2 or higher unexpected adverse events that have been reported; summary of all deaths occurring within 30 days for Phase I or II protocols; for gene transfer protocols, summary of all deaths while being treated and during active follow-up; any response information; audit results, and a summary provided by the study team. Other information (e.g. scans, laboratory values) will be provided upon request.

12.3 Monitoring

Involvement in this study as a participating investigator implies acceptance of potential audits or inspections, including source data verification, by representatives designated by the DF/HCC Overall Principal Investigator (or Protocol Chair) or DF/HCC. The purpose of these audits or inspections is to examine study-related activities and documents to determine whether these activities were conducted and data were recorded, analyzed, and accurately reported in accordance with the protocol, institutional policy, Good Clinical Practice (GCP), and any applicable regulatory requirements.

All data will be monitored for timeliness of submission, completeness, and adherence to protocol requirements. Monitoring will begin at the time of participant registration and will continue during protocol performance and completion.

13 REGULATORY CONSIDERATIONS

13.1 Protocol Review and Amendments

This protocol, the proposed informed consent and all forms of participant information related to the study (e.g., advertisements used to recruit participants) and any other necessary documents must be submitted, reviewed and approved by a properly constituted IRB governing each study location.

Any changes made to the protocol must be submitted as amendments and must be approved by the IRB prior to implementation. Any changes in study conduct must be reported to the IRB. The DF/HCC Overall Principal Investigator (or Protocol Chair) will disseminate protocol amendment information to all participating investigators.

All decisions of the IRB concerning the conduct of the study must be made in writing.

13.2 Informed Consent

All participants must be provided a consent form describing this study and providing sufficient information for participants to make an informed decision about their participation in this study. The formal consent of a participant, using the IRB approved consent form, must be obtained before the participant is involved in any study-related procedure. The consent form must be signed and dated by the participant or the participant's legally authorized representative, and by the person obtaining the consent. The participant must be given a copy of the signed and dated consent document. The original signed copy of the consent document must be retained in the medical record or research file.

13.3 Ethics and Good Clinical Practice (GCP)

This study is to be conducted according to the following considerations, which represent good and sound research practice:

- E6 Good Clinical Practice: Consolidated Guidance
www.fda.gov/downloads/RegulatoryInformation/Guidances/UCM129515.pdf
- US Code of Federal Regulations (CFR) governing clinical study conduct and ethical principles that have their origin in the Declaration of Helsinki
 - Title 21 Part 11 – Electronic Records; Electronic Signatures
www.access.gpo.gov/nara/cfr/waisidx_02/21cfr11_02.html
 - Title 21 Part 50 – Protection of Human Subjects
www.access.gpo.gov/nara/cfr/waisidx_02/21cfr50_02.html
 - Title 21 Part 54 – Financial Disclosure by Clinical Investigators
www.access.gpo.gov/nara/cfr/waisidx_02/21cfr54_02.html
 - Title 21 Part 56 – Institutional Review Boards
www.access.gpo.gov/nara/cfr/waisidx_02/21cfr56_02.html
 - Title 21 Part 312 – Investigational New Drug Application
www.access.gpo.gov/nara/cfr/waisidx_02/21cfr312_02.html
- State laws
- DF/HCC research policies and procedures
<http://www.dfhcc.harvard.edu/clinical-research-support/clinical-research-unit-cru/policies-and-procedures/>

It is understood that deviations from the protocol should be avoided, except when necessary to eliminate an immediate hazard to a research participant. In such case, the deviation must be reported to the IRB according to the local reporting policy.

13.4 Study Documentation

The investigator must prepare and maintain adequate and accurate case histories designed to record all observations and other data pertinent to the study for each research participant. This information enables the study to be fully documented and the study data to be subsequently verified.

Original source documents supporting entries in the case report forms include but are not limited to hospital records, clinical charts, laboratory and pharmacy records, recorded data from automated instruments, microfiches, photographic negatives, microfilm or magnetic media, and/or x-rays.

13.5 Records Retention

All study-related documents must be retained for the maximum period required by applicable federal regulations and guidelines or institutional policies.

13.6 Multi-center Guidelines

N/A

13.7 Cooperative Research and Development Agreement (CRADA)/Clinical Trials Agreement (CTA)

N/A

14 STATISTICAL CONSIDERATIONS

The study consists of a single stage of accrual of patients with hepatic metastases from colorectal cancer.

Patient safety will be assured by monitoring the number of patients who fail to receive the first six scheduled vaccinations because of toxicity. If three or more patients experience grade 4 or worse toxicity due to the vaccine before completing six immunizations, the study will be terminated. If the unknown true rate of grade 4 or worse toxicity is 0.05, then the probability of early termination is 0.04. Similarly, if the unknown true rate is 0.25, then the probability of early termination is 0.76.

Feasibility will be assessed by the ability to make vaccine from resected hepatic metastases in quantities sufficient for six vaccinations. Fifteen patients will be entered. If fewer than 9 patients receive six vaccinations, the study will cease. A success rate under 65% (true rate) may imply that the method needs further development or that the amount of tissue available in this population limits the feasibility of this strategy. This study will have 75% power against the null of 45% success rate, testing at the one-sided 0.18 significance level and using exact methods.

The percentage of patients who successfully receive 6 vaccinations and the number of vaccinations received by patients will be described. Any late occurrences of grade 3 or worse toxicity and the vaccination number at which they occur will be reported.

For the correlative science it is unclear which changes will occur in the circulating immune cells since a study like this has never been done in patients with resected hepatic metastases from colorectal cancer. Currently we do not have estimates to present a statistical model or plan. No changes in the correlative science should influence administration of the vaccine in the patients.

Table 1. 90% confidence intervals for the true proportion of patients who receive all six injections

Observed number of	Observed rate of patients	90% confidence interval for
--------------------	---------------------------	-----------------------------

patients who receive all six injections	who receive all six injections	the true rate of patients who receive all six injections
8	53%	(30%, 76%)
10	67%	(42%, 86%)
11	73%	(49%, 90%)
12	80%	(56%, 94%)

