3. PARTICIPANT SELECTION

3.1 Eligibility Criteria

Participants must meet the following criteria on screening examination prior to their planned liver resection to be eligible to participate in the study:

3.1.1 Stage IV patients must have:

- A) Histologically documented hepatic colorectal cancer metastasis
- B) Resectable hepatic lesion(s) as judged by PI or surgeon with the intent of an R0 resection.
- C) Primary tumor previously resected or planned resection at time of hepatic surgery

3.1.2 ECOG Performance Status 0 or 1

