5.1.2.2 All patients receiving at least one vaccination will be evaluable for toxicity. Patients will be considered evaluable for biologic activity if at least six vaccinations have been administered at a given dose level. There is no requirement for a particular number of patients at each cell dose level.

5.1.2.3 Vaccinations may be administered within 24 hours of the scheduled vaccine administration date (e.g. day 8, 15, 29) beginning with the day 8 vaccine.

5.1.2.4 Patients must be greater than 28 days from any chemotherapy, radiotherapy, immunotherapy, systemic glucocorticoid therapy, or resection of hepatic colorectal metastasis.

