6.3 Dose Modifications/Delays

6.3.1 There will be no dose adjustments for Grade 1 and 2 toxicities seen on this study.

6.3.2 If a patient develops grade 3 toxicity attributable to the vaccine, additional treatment will be withheld until all toxicity has resolved, then he or she may be retreated at monthly intervals. If the toxicity recurs with resumption of vaccine then the patient will be removed from study. If a patient develops a grade 4 toxicity attributable to the vaccine, he or she will be removed from study. If three grade 4 or greater toxicities attributable to the vaccine are observed at any time, the trial will be suspended to investigate the causes of these unexpected toxicities.

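### Section 14's safety-stopping probabilities (0.04 and 0.76) hold only if all 15 entered patients are vaccinated, and Sections 14 and 6.3.2 give different actions for the same three grade 4 events

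*Combined protocol and SAP*

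**What the plan says.** Section 14 sets the sample and the safety rule: "Fifteen patients will be entered", and "If three or more patients experience grade 4 or worse toxicity due to the vaccine before completing six immunizations, the study will be terminated". It gives a stopping probability of 0.04 at a true rate of 0.05, and adds that "if the unknown true rate is 0.25, then the probability of early termination is 0.76". It does not say how many vaccinated patients these figures assume.

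Other sections determine who can contribute an event:

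- Section 5.1.2.2: "All patients receiving at least one vaccination will be evaluable for toxicity". Section 14.3.2 says the same.
- Section 3.1 places screening before surgery: "Participants must meet the following criteria on screening examination prior to their planned liver resection". Section 1.1 enrols patients who are going to have a resection.
- Section 5.2.1.5 withholds vaccine if restaging scans show recurrence.
- Section 7.3 requires a minimum cell yield, and Section 14.3.1 makes the start of vaccination depend on harvesting enough viable cells.
- Section 14.3.1 provides for patients who never start because of progression or complications after surgery. It calls the plan feasible if at least 60% of enrolled patients begin vaccination.

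No section describes replacing unvaccinated patients.

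Section 6.3.2 has a three-event rule of its own: "If three grade 4 or greater toxicities attributable to the vaccine are observed at any time, the trial will be suspended", the stated aim being to investigate the causes.

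**The concern.** The stated probabilities treat 15 patients as being at risk of vaccine toxicity, but the plan assures only that 15 are entered. Whether vaccine can be made at all is listed among the primary endpoints in Section 14.1, so full vaccination cannot be taken for granted. With fewer patients at risk, the threshold of three is harder to reach at any given toxicity rate.

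Safety is the sole primary objective in Section 1.2, and 0.04 and 0.76 are the only safety-stopping probabilities in the plan. A reader would take 0.76 as the chance that the rule stops a study of a vaccine with a 25% grade 4 rate, without seeing that the figure is conditional.

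The two three-event rules raise a separate problem. If three patients have such toxicity before the sixth dose, staff who follow the document as written have two different instructions. That conflict does not affect the probabilities.

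**Working it through.** **Inputs.** Threshold of 3 patients, 15 entered, true rates 0.05 and 0.25, stated results 0.04 and 0.76 (all Section 14). Feasibility threshold of 60% of enrolled patients (Section 14.3.1). The number vaccinated, n, is not in the documents and is varied as an assumption.

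**Formula.** With n vaccinated patients, each with independent probability p of a qualifying toxicity:

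P(stop) = 1 − [(1−p)^n + n·p·(1−p)^(n−1) + C(n,2)·p²·(1−p)^(n−2)]

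**Step 1: reproduce the plan's figures with n = 15.**

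- p = 0.05: 1 − (0.46329 + 0.36576 + 0.13475) = 0.0362, which rounds to 0.04.
- p = 0.25: 1 − (0.0134 + 0.0668 + 0.1559) = 0.7639, which rounds to 0.76.

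At p = 0.25, n = 14 gives 0.72 and n = 16 gives 0.80. Only 15 patients at risk gives 0.76.

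**Step 2: number matching the feasibility threshold.** 0.60 × 15 = 9, provided that no patient is left out of that count for an unrelated withdrawal (Section 14.3.1).

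**Step 3: vary the number vaccinated, Section 14 safety rule alone.** For example, n = 9 and p = 0.25 gives 1 − (0.0751 + 0.2253 + 0.3003) = 0.3993.

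| Vaccinated (assumed) | P(stop), rate 5% | P(stop), rate 25% |
|---|---|---|
| 15 | 0.036 | 0.76 |
| 12 | 0.020 | 0.61 |
| 11 | 0.015 | 0.54 |
| 10 | 0.012 | 0.47 |
| 9 | 0.008 | 0.40 |

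For this rule to reach the same 0.76, the true rate would have to be about 31% with 12 vaccinated, 36% with 10 and 40% with 9.

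**Step 4: the same question by assumed start rate.** If each of 15 entered patients starts vaccination independently with probability q, the number of events is binomial with 15 patients and probability q·p. At rates of 5% / 25%, P(stop) is 0.028 / 0.69 for q = 0.9, 0.020 / 0.60 for q = 0.8 and 0.009 / 0.40 for q = 0.6.

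**Step 5: the two three-event rules side by side.**

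| | Section 14 | Section 6.3.2 |
|---|---|---|
| Unit | patients | toxicities |
| Window | before completing six immunizations | any time |
| Action | study terminated | trial suspended to investigate |

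Three patients with vaccine-related grade 4 or worse toxicity before the sixth dose satisfy both columns, and the stated actions differ. The document does not say that one rule is a tier of the other.

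**The case against.** **The arithmetic is right and the basis is conventional.** Quoting operating characteristics at the planned sample size is normal practice, and a reader can recover n = 15 from the figures. This stands: a reader might infer a calculation error, and there is none. The fault is an unstated condition. The 0.04 is also only improved by fewer vaccinated patients, since the chance of stopping at a 5% rate falls.

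**The share vaccinated is unknown.** This also stands. The documents do not say that the probability will be 0.61 or 0.40. The lower figures are a range over an assumption.

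**The rate could be defined per entered patient.** That would preserve 0.76, but it does not fit a rule about toxicity due to the vaccine or the evaluability definitions in Sections 5.1.2.2 and 14.3.2.

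**Other protections exist.** Section 6.3.2 also says "If a patient develops a grade 4 toxicity attributable to the vaccine, he or she will be removed from study", and Section 12.2 has the monitoring committee meet at least quarterly. Section 14 adds: "If fewer than 9 patients receive six vaccinations, the study will cease". A reader might infer from the table that the whole study is less likely to stop than 0.76, or alternatively that the feasibility rule makes up the loss. The documents support neither. They do not say when the feasibility rule is applied, and Section 5.5 lists reasons unrelated to toxicity for not completing six doses, so a combined stopping probability cannot be derived. Nor is 9 a floor: with 8 vaccinated the safety rule still has a probability of 0.006 / 0.32 of being met.

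**The two rules may be meant to differ.** Because a patient is removed after a grade 4 toxicity, counts of patients and of toxicities rarely diverge. The wider window could deliberately cover later events and second rounds (Section 5.3). A reader might infer three flat contradictions, but only the action in the overlap is a clear conflict.

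**Conclusion.** The point holds in two parts and should be fixed.

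First, 0.04 and 0.76 are correct for 15 vaccinated patients, a condition that the plan neither states nor assures. At a 25% rate, 0.76 is the upper limit for the Section 14 safety rule. It falls to 0.61 if 12 are vaccinated and to 0.40 if 9 are, about half the stated figure. This rests on independent patients with a common toxicity rate, on that rate being per vaccinated patient, on no replacement, and on an assumed number vaccinated. It describes this one rule and not the chance that the study stops for any reason.

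Second, Sections 14 and 6.3.2 prescribe different actions when three patients have vaccine-related grade 4 or worse toxicity before completing six immunizations. The differences in unit and window may be intended, but the document does not say so.

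**What to change.** - In Section 14, state that the stopping probabilities apply to patients given at least one vaccine, and that 0.04 and 0.76 assume 15 such patients.
- Add a short table of the probability at 5% and 25% for 9, 10, 11, 12 and 15 vaccinated.
- Reconcile Sections 14 and 6.3.2 on action, counting unit and time window. The sponsor decides how, including whether the two rules are meant as tiers. This review takes no position on which rule is right.

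The cost is protocol wording and one table, with no additional patients. The downside is that the stated safety-stopping probability will look less favourable.
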